4. TREATMENTS

4.1. Treatments Administered

In the Treatment Period, Cannabidiol Oral Solution will be dosed orally in three dose cohorts. Patients or parent/caregiver will be instructed how to measure, take their dose, and record their dose in the dosing diary when the IP is dispensed for the first time.

Total daily doses of 10, 20, or 30 mg/kg/day will be administered with food in two daily doses of 5, 10, or 15 mg/kg/dose approximately every 12 hours. Patients in Cohort 1 will be treated prior to initiation of enrollment into Cohort 2, and patients in Cohort 2 will be treated prior to initiation of enrollment into Cohort 3. Doses higher than 20 mg/kg/day will be titrated as described in [Section 4.4](#). Cannabidiol Oral Solution will be administered within 30 minutes after a meal, except during Visit 6 when fasting PK values will be obtained.

4.2. Identity of Investigational Product

The active pharmaceutical ingredient (API) in Cannabidiol Oral Solution is a pharmaceutical grade synthetic CBD manufactured according to cGMP. It is an off-white to pale yellow resin or crystal substance that is soluble in several organic solvents with an acid dissociation constant (pKa) of 9.64. The solution is a clear, colorless to pale yellow-brown colored solution (CBD concentration of 100 mg/mL) filled into a 30 mL amber glass vial. More detailed information may be found in the IB.¹

4.3. Method of Assigning Subjects to Treatment Groups

Eligible patients will be sequentially assigned to each dose cohort. That is, the first 10 eligible patients will be in Cohort 1, and so on.

4.4. Selection and Timing of Dose for Each Subject

Ten patients will be enrolled in each of three dose cohorts:

- Cohort 1: 20 mg/kg/day divided BID for 4 weeks.
- Cohort 2: 20 mg/kg/day divided BID for 5 days followed by 30 mg/kg/day divided BID for 4 weeks.
- Cohort 3: 10 mg/kg/day divided BID for 4 weeks.

Subjects will take each dose approximately every 12 hours with food in order to ensure consistent plasma levels are achieved, except for Visit 6 when blood for fasting pharmacokinetic analysis will be drawn prior to the morning dose. The date and time of all investigational product administrations will be documented in the case report form (CRF) from the seizure diary.

4.5. Blinding and Unblinding Treatment Assignment

Not applicable.

4.6. Treatment Compliance

The prescribed dosage, timing, and mode of administration of IP may not be changed unless there is a protocol-specified up titration or a safety concern or toxicity is identified for a patient.

The investigator, a member of the investigational staff, or a hospital pharmacist must maintain an adequate record of the receipt and distribution of all study medication using the Drug Accountability Form. These forms must be available for inspection at any time.

All supplies of IP should be accounted for at the termination of the study and a written explanation provided for discrepancies. All used and unused supplies, and packaging materials are to be inventoried and returned to the Sponsor or a designee by the investigator. The investigator is not permitted to return or destroy unused clinical drug supplies or packaging materials unless authorized by the Sponsor or a designee.

If the study is terminated, discontinued, suspended, or completed, all used and unused supplies of the investigational product may be destroyed via the use of a third-party vendor or be returned to the Sponsor or a designee after the final drug accountability check has been performed. A certificate of destruction will be provided to the Sponsor.

All regulations issued by the DEA concerning the accountability of Schedule I medications will be followed (e.g., prevention of diversion).

4.7. Permitted and Prohibited Therapies

4.7.1. Permitted Therapies

Any medications (other than those excluded by the protocol, see [Section 4.7.2](#)) that the investigator considers necessary for a patient's welfare and will not interfere with the investigational product may be administered at the investigator's discretion.

4.7.2. Prohibited Therapies

During the Screening, Titration, Treatment, and Follow-up Periods, patients are not to receive the following:

- Any cannabinoids besides the study drug (cannabidiol, Δ^9 -THC, hemp oil, Realm Oil or marijuana).
- Phenytoin, fluvoxamine, carbamazepine, or St. John's Wort.
- Medications that are strong inhibitors/inducers/sensitive substrates with a narrow therapeutic index for CYP3A4, CYP2C9, or CYP2C19 [Note: Stable doses of Valproic Acid during the screening, titration, treatment, and follow-up periods are permitted].
- Any other investigational drug or investigational device.
- Introduction of new anti-epileptic drugs (AEDs) or therapies (VNS, ketogenic diet) during the study is prohibited during the Treatment Period, but allowed during the Safety Period.

Although they are not prohibited, patients taking concomitant medications may need to be monitored with special care to identify any AEs arising due to the potential for altered drug metabolism.

4.8. Treatment After the End of Study

A final follow-up phone call will be conducted 14 days after completion of Visit 6 (End of Study).

Approved

5. STUDY DRUG MATERIALS AND MANAGEMENT

5.1. Labeling and Packaging

5.1.1. Labeling

The labels for the investigational product will contain all information according to regulatory requirements.

5.1.2. Packaging

The investigational product will be supplied in 30 mL containers of a 100 mg/mL strength (i.e., 3000 mg per container).

Non-proprietary or common name of drug product	Cannabidiol Oral Solution, 100 mg/mL
Dosage form	Oral solution
Strength	100 mg/mL

Please refer to the Cannabidiol Oral Solution IB¹ for additional information on the drug formulation.

The investigational product will be clearly marked according to FDA and/or ICH requirements regarding use for clinical study investigation only and will be labeled with the investigational product name, study reference number, storage conditions, and expiry date. It is the responsibility of the investigator to ensure that accurate accountability records are maintained throughout the study. Study center staff will dispense the investigational product according to the handling instructions.

5.2. Dispensing and Storage

IP will be stored at controlled room temperature (20 to 25 degrees Celsius, 68 to 77 degrees Fahrenheit) at the study centers.

Cannabis and its constituents (including CBD) are Schedule I controlled substances and subject to all applicable local and federal laws and regulations regarding these products. This includes security provisions for storing the controlled substances and for dispensing in a manner to prevent diversion. Additionally, the Sponsor or investigator must provide a statement of the quantity to be manufactured and the sources of the chemicals to be used or the substance.

The DEA regulations detail specific security requirements for storage of the investigational product. Licensed practitioners must store controlled substances in a "securely locked, substantially constructed cabinet" and must notify the DEA of the theft or significant loss of any controlled substances within one business day of discovering such loss or theft. Furthermore, all practitioners are prohibited from hiring employees who have been convicted of a drug-related felony or who have had a DEA registration denied or revoked.

Investigators are responsible for ensuring that all applicable licensures are in place and storage conditions are appropriate.

Doses of IP will be administered from the Schedule I-licensed study center.

The study centers are required to provide complete information, including case report forms (CRFs) and final outcomes, on all instances of addiction, abuse, misuse, overdose, drug diversion/drug accountability, discrepancies in amount of the clinical supplies of the investigational product, noncompliance, protocol violations, lack of efficacy, individuals lost to follow-up, and any other reasons why subjects dropped out of the study.

5.3. Drug Supply and Accountability

The investigator, a member of the investigational staff, or a hospital pharmacist must maintain an adequate record of the receipt and distribution of all study medication using the Drug Accountability Form. These forms must be available for inspection at any time.

All supplies of Cannabidiol Oral Solution should be accounted for at the termination of the study and a written explanation provided for discrepancies. All unused supplies and packaging materials are to be inventoried and returned to the Sponsor or a designee by the investigator. The investigator is not permitted to return or destroy unused clinical drug supplies or packaging materials unless authorized by the Sponsor or a designee.

If the study is terminated, discontinued, suspended, or completed, all unused supplies of the investigational product may be destroyed by via the use of a third-party vendor or be returned to the Sponsor or a designee after the final drug accountability check has been performed. A certificate of destruction will be provided to the Sponsor.

All regulations issued by the DEA concerning the accountability of Schedule I medications will be followed (e.g., prevention of diversion).

6. STUDY ASSESSMENTS

6.1. Efficacy Assessments

6.1.1. Video-Electroencephalography (Video-EEG)

A 4-hour video-EEG will be performed for all subjects at Baseline (Visit 2), Visit 5 (Week 4, Day 6) or the Early Withdrawal Visit. Hyperventilation will be conducted during the video-EEG. As overt clinical signs may or may not be present during the GSW bursts, response testing during the GSW bursts is encouraged, if possible, but not required.

Details regarding requirements for conducting the video-EEG and the independent central reader's review and assessment of the video-EEG is outlined in the EEG Charter.

6.1.2. Clinical Global Impression – Global Improvement (CGI-I)

The CGI-I will be assessed by the investigator at Visit 3, Visit 5 (Week 4, Day 6) or the Early Withdrawal Visit.

6.1.3. Seizure Diaries

Seizure diaries will be dispensed during the Screening Visit (Visit 1) to collect daily seizure activity throughout the Screening, Titration, and Treatment Periods, or the Early Withdrawal Visit. Each day, the patient or parent/caregiver will respond to the question: "How many absence seizures did the patient have today?"

6.2. Safety Assessments

Safety assessments for all patients will include medical history, physical examination, vital signs (seated blood pressure, pulse rate, temperature, and respiration rate), clinical laboratory testing (hematology, chemistry, and urinalysis), 12-lead ECG, concomitant AED blood levels, prior medication history (assessments of past/current AEDs and concomitant medications), C-SSRS, and AE assessments.

6.2.1. Demographics and Medical History

Each potential study participant will have the following assessments performed by the investigator or designee during the Screening Period (Days -28 to -1): demographic data, including sex, date of birth, race, ethnicity, medical/surgical history, estimate of historic seizure count from patient or parent, record of past and current AEDs, and concomitant medications.

6.2.2. Physical Examinations

A physical examination will be conducted for every patient during the Screening Visit (Visit 1). The examination will include evaluation of general appearance, skin, eyes, ears, nose, throat, neck, lymph nodes, chest, heart, abdomen, and extremities. Height and weight will be measured during Visits 1, 3, 6 (End of Study) or the Early Withdrawal Visit.

6.2.3. Neurological Examinations

A complete neurological examination (mental status, cranial nerves, nystagmus, motor system, sensory system, reflexes, coordination, gait, and station) will be conducted during Screening (Visit 1). A brief neurological examination will be conducted during Baseline (Visit 2), Treatment Period (Visits 3, 4, and Visit 6 [End of Study]) or the Early Withdrawal Visit.

6.2.4. Vital Signs

Vital signs (seated blood pressure, pulse rate, temperature and respiration rate) will be measured during Screening (Visit 1), Baseline Visit (Visit 2), Treatment Period (Visits 3, 4, and 6 [End of Study]) or the Early Withdrawal Visit.

Additional vital sign measurements may be performed as deemed medically necessary by research personnel.

6.2.5. Electrocardiograms

A resting 12-lead ECG will be conducted for every patient during Screening (Visit 1), Treatment Period (Visit 6 [End of Study]) or the Early Withdrawal Visit.

6.2.6. Clinical Laboratory Assessments

Blood samples for hematology and chemistry assessments will be collected during Screening (Visit 1), Treatment Period (Visits 3, 4, and 6 [End of Study]) or the Early Withdrawal Visit. Urine samples for urinalysis will be collected during Screening (Visit 1), Treatment Period (Visit 6 [End of Study]) or the Early Withdrawal Visit.

- Hematology: hemoglobin, hematocrit, total and differential leukocyte count, red blood cell (RBC), and platelet count.
- Chemistry: albumin, blood urea nitrogen (BUN), creatinine, total bilirubin, alkaline phosphatase (ALP), aspartate transaminase (AST), alanine transaminase (ALT), sodium (Na^+), potassium (K^+), chloride (Cl^-), lactate dehydrogenase (LDH), uric acid, glucose, and calcium.
- Urinalysis: pH, specific gravity, protein, glucose, ketones, bilirubin, blood, nitrite, leukocyte esterase, and urobilinogen. If protein, occult blood, nitrite, or leukocyte esterase values are out of range a microscopic examination will be performed.

Concomitant AED blood levels will be determined at Baseline (Visit 2), Visit 6 (End of Study), or the Early Withdrawal Visit.

6.2.7. Columbia Suicide Severity Rating Scale (C-SSRS)

The C-SSRS is a prospective assessment tool routinely used in studies of drugs with any potential for CNS effects. It captures the occurrence, severity, and frequency of suicide-related thoughts and behaviors during the assessment period. For patients aged 7 to 17 years and if the developmental level is appropriate, the questionnaire will be completed at Screening (Visit 1) and Visit 5 (Week 4, Day 6) or the Early Withdrawal Visit. For patients who are less than 7 years or for whom the C-SSRS is inappropriate due to the patient's developmental functioning, a

clinical assessment will be made following FDA guidelines.
<https://www.fda.gov/downloads/drugs/guidances/ucm225130.pdf>.

6.2.8. Adverse Events and Serious Adverse Events

6.2.8.1. Definition of Adverse Events

An AE is defined as any untoward medical occurrence in a patient administered a pharmaceutical product during the course of a clinical investigation. An AE can therefore be any unfavorable and unintended sign, symptom, or disease temporally associated with the use of an investigational product, whether or not thought to be related to the investigational product.

Patients will be monitored throughout the study for AEs. Monitoring for treatment-emergent AEs will begin as soon as the patient is dosed. All AEs must be followed until they are resolved or stabilized, or until all attempts to determine resolution of the event are exhausted. The investigator should use their discretion in ordering additional tests as necessary to monitor the progress of such events.

An AE may be:

- A new illness, not documented in the patient's medical history;
- Worsening of a concomitant illness;
- An effect of the study medication; it could be an abnormal laboratory value, as well as a significant shift from baseline within normal range which the qualified investigator or medical qualified designate considers to be clinically important;
- A combination of two or more of these factors.

Surgical procedures themselves are not AEs. They are therapeutic measures for conditions that required surgery. The condition for which the surgery is required is an AE, if it occurs or is detected during the study period. Planned surgical measures permitted by the clinical study protocol and the conditions(s) leading to these measures are not AEs, if the condition(s) was (were) known before the start of study treatment. In the latter case, the condition should be reported as medical history.

Absence seizures will not be considered AEs. However, new seizure types and injury resulting from a seizure will be captured as AEs.

Patients will be monitored throughout the study for AEs. All AEs must be followed until they are resolved or stabilized, or until all attempts to determine resolution of the event are exhausted. The investigator should use his/her discretion in ordering additional tests as necessary to monitor the progress of such events.

Adverse events reported prior to dose administration will be recorded as part of the patient's medical history.

Previous clinical trial experience has shown that somnolence, diarrhea, and transaminase elevations may be associated with CBD treatment. Therefore, Insys Development Company has identified these as Adverse Events of Special Interest.

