In addition, a long-term safety study (Protocol INS011-14-030) for subjects enrolled in the PK study above was recently completed. Fifty-two of 61 subjects from INS011-14-029 enrolled; 45 subjects completed the study. There were seven early termination subjects (two for withdrawal of consent, two for AEs of aggressions and sleepiness/irritability, one for the SAE of worsening seizures, one for lack of efficacy, and one subject with a genetic mutation died from systemic sepsis and multi-organ failure considered nonrelated). Overall, 91% of the subjects were taking doses greater than 20mg/kg/day, with 38% of subjects tolerating 40mg/kg/day. The most common drug-related AEs reported were anemia (5 subjects), somnolence (4 subjects), and weight increased (4 subjects). However, the weight increases ranged from a little over 2 lbs to approximately 7 lbs.

During the study, trough PK values were drawn and interim PK data for CBD and 7-OH CBD from Visit 5 (Week 4) to Visit 8 (Week 24) were analyzed. Dose-normalized mean trough CBD concentrations ranged from 11.9 to 16 (ng/mL)/(mg/kg), showing relatively stable levels for up to 6 months dosing Cannabidiol Oral Solution at various dose levels. After one month of dosing, there did not appear to be much accumulation, even though early accumulation had likely happened when compared with INS011-14-029 results. High variability in trough CBD concentrations was observed, but the extent of variability between visits was similar as reported in the previous 029 study.

An open-label study of Cannabidiol Oral Solution (20 mg/kg/day and 40 mg/kg/day) in pediatric subjects with infantile spasms refractory to ACTH and vigabatrin recently was halted due to futility (Protocol INS011-15-054) because only one out of nine patients achieved a complete response.

A food effect study of Cannabidiol Oral Solution in normal healthy adults (Protocol INS011-15-043) recently completed and the results are presented in the IB. Analysis demonstrated significantly higher CBD levels when administered with food.

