6.2.8.4. Definition of Serious Adverse Events

A serious AE (SAE) is any AE that fulfills any of the following criteria, as per 21 CFR 312.32:

- Results in death;
- Is life-threatening;
- Requires in-patient hospitalization or prolongation of existing hospitalization;
- Results in persistent or significant disability or incapacity;
- Is a congenital anomaly or birth defect;
- Is medically significant or requires intervention to prevent one of the outcomes listed above.

Serious AEs will be captured from the time of consent through the end of the study.

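### As worded, an absence seizure that meets a seriousness criterion is neither an AE nor an SAE, and it is left unclear whether worsening of absence seizures is reportable

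*Protocol*

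**What the plan says.** Protocol Section 6.2.8.1 opens with a broad definition: "An AE is defined as any untoward medical occurrence in a patient administered a pharmaceutical product during the course of a clinical investigation". Among the forms that an AE may take it lists "Worsening of a concomitant illness" and an effect of the study medication. Further down it takes the study disease's own events out and sets the boundary: "Absence seizures will not be considered AEs. However, new seizure types and injury resulting from a seizure will be captured as AEs".

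Section 6.2.8.4 makes the serious category a subset of the AE category: "A serious AE (SAE) is any AE that fulfills any of the following criteria". One of those criteria is "Requires in-patient hospitalization or prolongation of existing hospitalization".

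Section 6.2.8.7 requires sites to notify the sponsor at once of any SAE and to send the SAE form within 24 hours of first knowledge. Section 8.6.4.1 limits AE summaries to treatment-emergent AEs; the separate SAE and AE-discontinuation summaries draw on the same records.

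On earlier experience, Section 1.3 reports seven early terminations among 52 patients in the sponsor's long-term study of this product, including "one for the SAE of worsening seizures".

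**The concern.** Leaving out expected events of the disease under study is common and sensible here. Section 1.4 notes that these children have many absence seizures a day, and Section 8.1 makes the EEG count an efficacy endpoint. Recording each one as an AE would swamp the safety data.

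The difficulty is that the exclusion is absolute. It does not separate a patient's habitual absences from one that puts the child in hospital. Since an SAE must first be an AE, removing the event at the first step also removes it at the second, where expedited reporting begins.

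What is at stake is the completeness of safety reporting for children taking an investigational add-on drug. A serious event in the target disease could go unreported by a site that follows the text exactly. Sites that report it anyway would be applying a different rule, so the AE and SAE tables by dose would depend partly on how each of about eight sites reads one sentence.

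**Working it through.** The protocol gives no figure on this point, so there is none to reproduce. The check is a reading of the sections in sequence.

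1. **Is the exclusion qualified?** Section 6.2.8.1 excludes absence seizures and then names two things that remain reportable: new seizure types and injury from a seizure. Frequency, duration, severity and seriousness are not mentioned. With the exceptions listed, a reader will take what is not listed as excluded. The surgery rule in the same section, by contrast, is conditional: the underlying condition escapes AE status only if it was known before study treatment began.

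2. **Does the SAE definition bring the event back?** No. Section 6.2.8.4 starts from events that are already AEs and adds a seriousness criterion. Take an absence event that needs hospital admission, with no injury and no new seizure type:
   - Section 6.2.8.1: not an AE.
   - Section 6.2.8.4: SAE = AE + criterion. The criterion is met, the AE condition is not, so it is not an SAE.
   - Section 6.2.8.7: the 24-hour form applies to SAEs, so it is not triggered.
   - Section 8.6.4.1: the summaries draw on AE records, so the event is absent.

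3. **Does another section restore it?** None does. The causality, recording and follow-up rules (Sections 6.2.8.3, 6.2.8.7 and 6.2.8.8) all start from an event already classed as an AE or SAE.

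4. **How firm is the conflict within Section 6.2.8.1?** The worsening item refers to a concomitant illness. Childhood absence epilepsy is the study disease and fits that term only loosely. The firmer tension is between the general definition, which covers any untoward occurrence, and an exclusion that ignores how untoward the occurrence is.

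5. **Where would worsening be seen?**
   - Daily diary (Section 6.1.3): yes, as a count. It is dispensed at Screening, so there is a baseline count. It does not ask about duration or severity.
   - CGI-I at Visits 3 and 5 or Early Withdrawal (Section 6.1.2): possibly, as a global impression.
   - Video-EEG at Week 4 or Early Withdrawal (Section 6.1.1): yes, as a count.
   - Reasons for withdrawal by treatment group (Section 8.6.1.1): yes, if the patient leaves for that reason.

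   The first three are listed as efficacy assessments and the fourth as disposition. None carries expedited reporting.

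6. **The earlier study.** 1 of 52 = 1.9%. Section 1.3 does not state the seizure type. The patients came from a study of mixed treatment-resistant seizure disorders with doses up to 40 mg/kg/day, in which tonic seizures were thought the most representative. The present trial enrols absence epilepsy, excludes other active nonfebrile seizure types and does not exceed 30 mg/kg/day.

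**The case against.** The strongest reply is that a specific exclusion from a general definition is not a contradiction. The text excludes absence seizures, meaning individual events, and not aggravation of the epilepsy. An investigator could report worsening as an untoward occurrence, as an effect of the drug or, if the study disease counts as a concomitant illness, under the worsening item. Worsening would also be seen: the diary is reviewed at Week 2 as part of medical status together with vital signs, neurological examination and AEs (Section 3.1.1); an EEG is required at Early Withdrawal; and Section 5.2 obliges sites to report lack of efficacy and any other reason for dropping out.

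Much of this stands. It makes worsening ambiguous, not excluded by rule, and it means that a case ending participation would probably be visible by dose group. It does not answer the serious single event. There the excluded item is the seizure itself, and visibility in a diary or disposition table does not start the 24-hour report.

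Three stronger readings are tempting and the protocol does not support them:

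- *No worsening can ever be captured.* Other routes exist, and the wording does not clearly bar an investigator from reporting aggravation of the disease.
- *Aggravation of absence seizures by this product is already established, at about 2%.* The single earlier SAE names no seizure type and arose in a different population. It shows only that seizure worsening was recorded as an SAE with this product.
- *The ongoing safety review will not see such events.* Sections 3.1.1 and 6.2.8.9 refer to available safety data and leave the detail to the Data Monitoring Charter, which is not at hand. The charter may or may not include diary data.

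**Conclusion.** The point holds in two parts of unequal strength.

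For an absence event that meets a seriousness criterion without injury or a new seizure type, the result follows from the text: it is outside AE, SAE, expedited reporting and the AE tables. This assumes only that sites apply Sections 6.2.8.1 and 6.2.8.4 as written.

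For clinically important worsening that is not serious, the protocol is unclear. The data would probably exist, but not clearly as safety data.

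The size cannot be put as a rate. The protocol gives no frequency for serious or worsening absence events, and 1 of 52 does not supply one. With ten patients per cohort, one unrecorded patient would change a dose group's incidence by 1/10 = 10 percentage points. That is arithmetic on the cohort size and not evidence that such a case will occur or be missed.

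This is a flaw in a stated rule, not a detail left for the statistical analysis plan, and it should be corrected because the gap affects serious events and closing it is cheap.

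**What to change.** Reconcile Sections 6.2.8.1 and 6.2.8.4 by qualifying the exclusion:

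- Absence seizures consistent with the patient's usual pattern are not AEs.
- Any absence event that meets a criterion in Section 6.2.8.4 is recorded as an SAE and reported under Section 6.2.8.7.
- Worsening that the investigator judges clinically important is recorded as an AE. For frequency, the comparison is the daily count against the Screening diary. For duration or severity it is clinical judgement against the patient's history, because the diary does not record either.
- New seizure types and seizure-related injury remain AEs, as now.

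Repeat the rule in the CRF completion guidance so that all sites apply it alike. This changes a reporting definition only and touches no dose or treatment rule. The cost is one sentence in the protocol, a matching line of CRF guidance and a few more AE records.
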